## Randomisation

The level of randomisation is at the local authority level. Due to the stepped-wedge evaluation design, we randomise the order in which local authorities implement the programme, in six month intervals, rather than which local authority implements the model. The randomisation will be stratified by the level of readiness of participating local authorities. Each local authority will be classified as either 'high readiness', for those that are in a position to implement the model sooner, and second for the 'low readiness' authorities, for those that will need longer to implement the model. Two local authorities were identified as 'high readiness', and three as 'low readiness'.

The two local authorities classified as 'high readiness' will be randomly assigned to implement the model either first or second. Those classified as 'low readiness' will also have the order randomised in which they will implement the model, following the high readiness local authorities (so they will be the third, fourth, and fifth local authorities to implement the model).

The division of local authorities into more or less ready tranches is meant to avoid implementation failure caused by choosing local authorities to receive the intervention that are not yet ready. The assessment of readiness was conducted by the developing local authority Hertfordshire in collaboration with the Department for Education (DfE). Our strata are thus very small strata (2-3), which normally would be avoided but was necessary in order to be able to implement the evaluation. However it is a notable constraint on our randomisation, that will affect the robustness of our results. This will be reflected in the evidence strength rating awarded to the final study.

To avoid potential contamination, local authorities whose implementation start date has not yet passed have to commit to business-as-usual practices to enable a treatment and control group comparison in each time period. However, they will be given permission to begin preparation to implement, so long as it would not influence the current practice in the local authority.

For the purposes of this RCT, we will only consider children who have been in touch with children's social care between six-months before the first local authority's implementation date, and six-months after the last local authority's implementation date. We define the implementation date as the date the Family Safeguarding model is considered 'Operationally Live' in the local authority. The Operationally Live date has been set in advance by the Department for Education. When analysing the data, we may change the date we consider the intervention to have gone Operationally Live, if it becomes apparent that there have been significant changes in terms of the timings of the models core activities. This will only be done with the agreement with the Department for Education and consultation with the model developer. Any such changes will be detailed in the report. Specifically, the core activities are as detailed below.

[figure not shown]
By the Operationally Live date:

- Training in Motivational Interviewing and workshops by the model developers should have been delivered to all staff in family safeguarding teams.
- Specialist adult workers should be recruited and in post.

From the Operationally Live date:

- Staff should be using Motivational Interviewing and the parenting assessment and intervention programme with families,
- Staff should be recording case notes using the electronic workbook
- Group case supervision should begin taking place at regular intervals for cases with adult specialist worker involvement.

The diagram below illustrates the randomisation and intended timings of the implementation of Family Safeguarding across the local authorities. The trial period, as indicated in the diagram, takes place from 6 months prior to when the first local authority implements the model (or goes Operationally Live), and continues until 6 months after the final local authority implements the model.

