There is a risk of non-compliance, e.g. local authorities may implement some or all aspects ahead of their agreed Operationally Live date, or fail to implement some elements. As stated above, we will adjust the date we consider Family Safeguarding has been implemented, if it

---

 Population as described above.

 We consider the referral date to be the relevant date according to which the relevant time dummy is determined.

 Children can only occur once in our evaluation, i.e. that we consider the first referral.

becomes apparent that there have been significant changes in terms of the timings of the models core activities. This will only be done with the agreement of the Department for Education and in consultation with the model developer. However, outside of this we will take an intention-to-treat approach, and will not, in our primary analysis consider other elements of non-compliance. However if the IPE shows that there have been substantial instances of non-compliance, we will consider running complier average causal effect (CACE) analysis to account for this. This would however be secondary analysis.

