Allegiance Bias (IPE)	Low	High	
Funding for the evaluation is provided by the Department for Education (DfE). WWCSO must work closely with the authorities who developed the intervention, the authorities introducing the intervention, and the funder of rollout (DfE), in order to deliver the project. This could result in a risk to the independence, or perceived independence of the evaluation.
 
However, in mitigation of this risk, WWCSO are a separate and independent organisation, with their own separate governance processes - a board of trustees whose role includes oversight of the independence of the organisation. Further, WWCSO will act as a data controller for this evaluation. Therefore, the way in which the data is processed is determined by WWCSO and not any other organisation. In addition, the WWCSO evaluators come from a neutral standpoint, informed by the current state of the evidence. There is so far no evidence of impact of the model relative to a robust counterfactual, and the model is therefore in a position of equipoise. The publication of a protocol in advance of data collection will also ensure that the evaluators follow a pre-planned approach, providing full transparency of methods and rationale. In addition, as stated in the qualitative analysis methods, consideration will be given to contrasting and inconsistent accounts, and quotes and triangulation across informants and methods will be used to support findings that are reported. Finally, researchers will aim to reassure participants that identifying information will not be shared outside of the research organisation - providing families and staff an opportunity to speak more freely and openly than they might do otherwise.

Data is not available in required format (RCT)	Medium	High	We will send a draft data-collection template to local authorities far in advance, and consult with relevant data teams at local authorities to ensure they understand and are able to provide the data we need. If they are not able to do at initial consultation, we will support them to ensure that they can by the time outcome data is available.

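### The date that puts each child in treatment or control may be moved at the analysis stage, with no rule that this be settled before, or blind to, outcome data

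*Protocol*

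**What the plan says.** The Conditions section assigns each child to treatment or control by whether the model was running in the authority at the child's first referral in the trial period. The start of the model is the Operationally Live date. On that date the Randomisation section says:

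- Origin of the date: "The Operationally Live date has been set in advance by the Department for Education".
- Power to revise it: "When analysing the data, we may change the date we consider the intervention to have gone Operationally Live", the condition being "if it becomes apparent that there have been significant changes in terms of the timings of the models core activities". Five core activities are then listed.
- Who must be involved: "This will only be done with the agreement with the Department for Education and consultation with the model developer".
- Disclosure of a revision: "Any such changes will be detailed in the report".

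The Primary Analysis section repeats the date rule for the main model, with the same governance, and then adds that "outside of this we will take an intention-to-treat approach".

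The Risks table rates a significant change of implementation date as medium likelihood and low impact, and gives the protocol's flexibility as the mitigation. The Data gathering table has outcome data arriving from the end of the trial period, in 18-month intervals, for a further 36 months.

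**The concern.** In a stepped wedge the crossover date is the exposure variable. Moving it switches a block of children from one arm to the other in the periods next to the step. Using actual rather than planned crossover dates can be legitimate, but only if they are fixed without knowledge of the outcomes.

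Here the decision is placed at analysis, when outcomes can be in hand. The trigger is qualitative, and the plan does not say how the new date is to be picked once the trigger is met. The date also bounds the trial period (six months before the first implementation date to six months after the last), so moving the first or last authority's date can change who is in the sample as well as who counts as exposed.

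No planned analysis would show the effect of a move:

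- The alternative treatment definitions in the Sensitivity Analysis count time since the authority implemented the model.
- The differential time effects model counts periods since implementation.
- The permutation test is not tied to any stated set of dates.

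All of these can inherit a revised date. None commits to the dates first set.

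**Working it through.** **Inputs** (MDES table and Appendix B): baseline 0.06; ICC 0.00722; 1,700 children per authority per six-month period; 5 authorities, one per step; 6 periods; two-sided alpha 0.05; power 0.8.

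**Step 1. Reproduce the plan's MDES.** The Hussey–Hughes variance is

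Var = Iσ²(σ² + Tτ²) / [(IU − W)σ² + (U² + ITU − TW − IV)τ²]

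- Total variance: 0.06 × 0.94 = 0.0564.
- τ² = 0.00722 × 0.0564 = 0.000407.
- σ² = 0.99278 × 0.0564 / 1,700 = 0.0000329.
- I = 5, T = 6, U = 15, W = 55, V = 55, so IU − W = 20 and the τ² multiplier is 225 + 450 − 330 − 275 = 70.
- Var = 0.00001398, SE = 0.00374.
- MDES = (1.960 + 0.842) × 0.00374 = 0.0105, which matches the protocol.

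**Step 2. How many children a move reclassifies.** The 3-month shift is an assumption; the protocol gives no size.

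- One authority: 1,700 / 2 = 850 children.
- All five: 5 × 850 = 4,250, which is 4,250 / 51,000 = 8.3% of the sample.

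**Step 3. Effect on type I error.** I simulated trials with no treatment effect, using 5 authorities × 12 quarters, 850 children per cell, the variances above treated as known, and a generalised least squares z-test. The analysis was run on every date set allowed in a scenario and the most extreme result kept. I ran 40,000 trials, once with quarterly and once with six-month time effects.

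| Date sets allowed | Two-sided error | Error favouring the model |
|---|---|---|
| Original dates only | 5.0% | 2.5% |
| Original, or one 3-month delay in one given authority (2 sets) | 6.8–7.0% | 3.4–3.5% |
| One given authority, 3 months either way (3 sets) | 8.3–8.5% | 4.1–4.3% |
| Any one of the five, 3 months either way (11 sets) | 15–16% | 8% |
| Any authorities delayed 3 months (32 sets) | 21–22% | 11% |
| All free to move 3 months either way (243 sets) | 48–49% | 24–25% |

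Rows two and three hold for whichever authority is chosen. The rise in row two is modest because the z statistics on the original and the delayed date are highly correlated (about 0.91 to 0.92).

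**Step 4. Can the decision be locked in time?** On the indicative Timeline the last authority goes live in Apr-22 and its 3-month process-evaluation data fall in Jul-22. The trial period ends six months after go-live, about Oct-22, and outcome extracts start then. Delivery data for every authority therefore exist before the first outcome extract. That extract could already hold complete 18-month outcomes for children referred up to about Apr-21, a span that includes the first two authorities' steps (Apr-20 and Oct-20).

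**The case against.** The strongest defence is that the rule is tied to delivery, not to outcomes. A change needs a significant shift in the timing of listed activities, all parties are asked to report such shifts, the process evaluation should pick them up, and any change is disclosed. Treatment condition is collected at twelve-month intervals during the trial, so exposure is largely recorded before outcomes arrive. Child-level data are restricted to the evaluator's research team, so nothing shows the funder or developer seeing outcomes when a date is agreed. A numeric trigger could reasonably be left to a statistical analysis plan.

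Much of this stands, and it limits the point in several ways:

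- A reader might take 48%, or even 15%, as the error this plan will produce. The documents do not support that. Those figures need free choice of which authorities move and in which direction, whereas the protocol requires a timing change in the authority concerned. The realistic case is one documented alternative date for one authority.
- A reader might say intention-to-treat is broken. The protocol claims it only outside the date rule. This is an exception carved out of the principle, not a contradiction of it.
- A reader might infer that the developer can veto a date. The developer is only consulted. The funder must agree, which also restrains a unilateral change by the party holding the data.
- A reader might infer that results will be consulted. The protocol does not say so; it merely does not prevent it.
- The Randomisation section randomises the order of implementation and the Design section speaks of randomising the start date. A 3-month move of one authority leaves the order intact.

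What the defence does not supply is a lock. None of these safeguards fixes when the decision is taken or what is known at that moment.

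**Conclusion.** The point holds as a gap in pre-specification. The date that defines the primary exposure may be changed during analysis, on an unquantified trigger, with no outcome-blind cut-off and no parallel analysis on the dates first set. Disclosure lets a reader see that a date moved, but not what the result would have been otherwise.

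The plausible size is modest: two-sided error of about 7% to 8% instead of 5%. The figures of about 15%, 22% and 48% are ceilings for an unrestricted search. All rest on an assumed 3-month shift, no true effect, the more extreme result always being chosen, and a linear model with known variances in place of the planned logistic mixed model. If dates are fixed before outcomes are seen, error from this source stays at 5% and the MDES stays at 0.0105. The point concerns how children are classified in the analysis, not when or how the model should be introduced.

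**What to change.** In the Randomisation section, strike the opening clause that places the decision at the analysis stage, and align the Primary Analysis section. State instead that:

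1. Any revised Operationally Live date is decided only from process-evaluation and delivery records, judged against the core activities already listed, and blind to outcomes.
2. The decision and its reasons are posted on the Open Science Framework before the first outcome extract from any authority (about Oct-22 on the indicative Timeline). No date changes after that.
3. The primary model on the originally set dates is always reported alongside.

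The funder's agreement and the developer's consultation can stay, provided both are given before the lock and without sight of outcomes.

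The cost is one paragraph and one extra model run. The information needed is due by Jul-22, so the lock need not delay the evaluation.

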## Context

The IPE and RCT parts of the evaluation will be undertaken in the local authorities funded by the Department for Education to introduce Family Safeguarding as part of the Strengthening Families, Protecting Children programme, with the exception of the Trailblazer who is participating in a separate pilot evaluation. These local authorities are due to launch Family Safeguarding at six-month intervals beginning in April 2020. In the order they will be rolled out, these local authorities are Walsall, Lancashire, Telford & Wrekin, Wandsworth and Swindon.

All authorities had a judgement of ‘requires improvement to be good’ at the point at which they applied for the programme. However, at the point of rollout to the first local authority, Children’s Services in three of these authorities (Walsall, Lancashire and Wandsworth) have an Ofsted judgement of ‘requires improvement to be good’, while Swindon received a

judgement of 'good' in July 2019 and Telford & Wrekin received a judgement of 'outstanding' in January 2020. These authorities were selected by the Department for Education to participate in the programme due to having high rates of children looked after compared to their local authority statistical neighbour median over the last 3 years, and/or rising rates of children looked after in each of the last 3 years.

York Consulting is currently conducting a process evaluation of Family Safeguarding in four additional local authorities, namely Peterborough, Luton, Bracknell Forest and West Berkshire.

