## Analysis plan

### Primary Analysis

We will assess the impact of Family Safeguarding Model on the primary outcomes of interest  $Y_{iat}$  in the following GLMM regression framework:

$$\text{logit}(Y_{iat}) = \beta_0 + \alpha_{0a} + \beta_1 FS_{iat} + \sum_{i=1}^5 \beta_{i+1} I(t = i) + \gamma X_{iat} + \rho Z_{at} + \varepsilon_{iat}$$

Where

- $Y_{iat}$  is a binary indicator that equals 1 if the child entered care within 24 months of their first referral in the trial period, and 0 otherwise.
- $\alpha_{0a}$  is a (normally distributed) random intercept at the level of the cluster. This random effect estimates the stochastic variation of individual clusters around the conditional mean of the clusters.
- $\beta_2 - \beta_6$  are a series of indicator variables adjusting for time trends by introducing dummy variables for each time after the baseline period  $t = 0$ .
- $FS_{iat}$  is a binary indicator that is equal to 1 if the child had its first referral during the trial period after the local authority implemented Family Safeguarding (and 0 if before).
- $X_{iat}$  is a vector of individual and household level characteristics that may also influence the outcome, such as age of the child, gender, and household SES.
- $Z_{at}$  is a vector of time-varying local authority characteristics, such as the number of children per local authority or the turnover rate of staff.
- $\varepsilon_{iat}$  are the errors at time  $t$  for individual  $i$ .

The GLMM is an extension of the GLM for analysing correlated data. The unit of analysis is at the individual level to optimise the power to detect an effect within the constraints of the project. We use a logistic regression within the GLMM framework to account for the binary nature of our outcome variable and because the baseline rate is low.

We will judge the statistical significance of the treatment effects applying a significance level of 5%. Due to the small number of clusters, we cannot cluster or bootstrap standard errors via any conventional method. However, we will consider whether or not applying a wild bootstrap with a correction for the small number of clusters is appropriate in this instance. Our sensitivity analysis will consider different evaluation approaches that are discussed in detail below.

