## Timeline

		-3m	0m	3m	12m	24m
	LA	IPE Baseline	Operationally Live	IPE 3m Follow-up	IPE 12m Follow-up	IPE 24m Follow-up
1	Walsall	Mar-20	Apr-20	Jul-20	Apr-21	Apr-22
2	Lancashire	Jul-20	Oct-20	Jan-21	Oct-21	Oct-22
3	Telford & Wrekin	Jan-21	Apr-21	Jul-21	Apr-22	Apr-23
4	Wandsworth	Jul-21	Oct-21	Jan-22	Oct-22	Oct-23
5	Swindon	Jan-22	Apr-22	Jul-22	Apr-23	Apr-24

\*This timetable is indicative only. Evaluation dates may be subject to change in line with changes to delivery timescales

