Implementation date changes significantly (RCT)	Medium	Low	
Changes to the implementation date, if not taken into account in the analysis, could significantly undermine the analysis. We have mitigated against this by allowing for some flexibility within the trial protocol. See the section on randomisation above for details.
 
In order to be able to take any changes out in our analysis, we have been clear that it is important that all parties clearly communicate with us. In addition this should be picked up in the process evaluation.
 
Significant changes could also delay outcome data, and so reporting.

Implementation happens over time, not allowing for precise definition (RCT)	Medium	Medium	If the key components of the model are delivered across a wide time-period, it could be difficult to determine when to classify children as treatment or control. In the Randomisation section we try to provide some clarity for how we will do this; in addition our sensitivity analysis should help somewhat. However it would remain that this could bias our treatment estimate.
Lack of fidelity or inconsistencies in implementation (RCT)	Medium	Low	This could obscure what it is we are evaluating. The IPE will explore how the model was delivered in the different local authorities, so will allow us to contextualise the findings.
Unanticipated changes in local authorities (RCT)	Medium	Medium	Such as changing in assessment thresholds, could bias our results. Our IPE should help us know whether this is the case. We also have determined in our analytical strategy that we would add dummy covariates for implementing other models during the trial period.

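### If a go-live date is changed and falls inside a six-month period, the period dummies no longer fully remove time effects shared by all authorities; a fixed window start and month-of-referral effects would remove them

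*Protocol*

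**What the plan says.** Under Context, the authorities are "due to launch Family Safeguarding at six-month intervals beginning in April 2020", and under Randomisation, "we randomise the order in which local authorities implement the programme, in six month intervals". The planned go-lives in the Timeline are April 2020, October 2020, April 2021, October 2021 and April 2022, with the note "This timetable is indicative only".

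The window is tied to the first and last go-live: it "takes place from 6 months prior to when the first local authority implements the model (or goes Operationally Live), and continues until 6 months after" go-live in the last authority. The Data gathering table ends the baseline period on the date the first authority goes live.

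Randomisation also states that, at analysis, "we may change the date we consider the intervention to have gone Operationally Live" if the timing of core activities has changed significantly. This needs the funding department's agreement and consultation with the developer. Primary Analysis repeats it: "we will adjust the date we consider Family Safeguarding has been implemented".

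The primary model handles time through "indicator variables adjusting for time trends by introducing dummy variables for each time after the baseline period": five dummies, set by referral date. The treatment indicator also follows the referral date, so it can switch inside a period. The Risks table rates a significant date change as Medium likelihood and Low impact: "We have mitigated against this by allowing for some flexibility within the trial protocol".

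**The concern.** Period dummies remove common time effects completely only if treatment status is constant within each authority-by-period cell. The planned schedule meets this condition because every go-live is a period boundary. A go-live moved by a number of months that is not a multiple of six breaks it in that cell. The control referrals there come from the first part of the period and the treated referrals from the second. Any shared movement between the two parts is then counted partly as treatment effect.

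The moving window can spread the problem. If the first go-live is changed, and the window and six-month periods move with it, the other four go-lives fall mid-period although their own dates did not change. Referrals are also dropped in those authorities, and some children's first referral in the window changes.

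The risk is to the comparison that the stepped-wedge design exists to protect. It arises even when the date change is correct and made without sight of outcomes.

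**Working it through.** **Inputs.** From Sample size / MDES calculations and Appendix B: rate 0.06, ICC 0.00722, 1,700 children per authority per six months, 5 authorities, 6 periods, two-sided alpha 0.05, power 0.80. From the Timeline: go-lives at months 6, 12, 18, 24 and 30 of a 36-month window (month 0 = October 2019). Assumptions not in the documents: referrals spread evenly over months (1,700/6 = 283.3 per authority-month), true effect zero, linear model, illustrative three-month delays.

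**Reproducing the plan.** The Hussey-Hughes variance with these inputs and MDES = (1.96 + 0.84) x SE gives 0.01048, against 0.0105 stated. 1,700 x 5 x 6 = 51,000. With the planned dates the leak is 0.

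**Leak formula.** With authority effects and period dummies, only within-period movement of the common time function f can leak:

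leak = N / S

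N is the sum, over treated months in cells where treatment switches mid-period, of f minus its period mean. S is the residual sum of squares of the treatment indicator over authority-months:

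S = (treated months) - (authority totals squared / months per authority) - (period totals squared / authority-months in the period) + (grand total squared / all authority-months).

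- *Linear trend of 1 unit per six months:* a switch at the middle of a period contributes (0.5 + 1.5 + 2.5)/6 = 0.75.
- *July-September dip of depth 1:* a mid-period switch contributes 3 x (-0.5) = -1.5 in an April-September period, +1.5 in a July-December period, and 0 in October-March or January-June.

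**A. First authority 3 months late, planned grid kept.** Treated months 27, 24, 18, 12, 6 (total 87).
S = 87 - 1,809/36 - 1,953/30 + 87²/180 = 87 - 50.25 - 65.10 + 42.05 = 13.70.
Trend: 0.75/13.70 = 0.055. Dip: -1.5/13.70 = -0.109.

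**B. Same delay, window and six-month periods re-anchored to the new first go-live.** The window is 33 months and the last period is half-length. It drops 3 x 5 x 283.3 = 4,250 referrals, leaving 46,750. The other four authorities switch mid-period.
S = 87 - 1,809/33 - (1,476/30 + 225/15) + 87²/165 = 87 - 54.82 - 64.20 + 45.87 = 13.85.
Trend: 4 x 0.75/13.85 = 0.217. Dip: 2 x 1.5/13.85 = 0.217.

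**C. All five 3 months late, planned grid kept, 36 months.** Treated months 27, 21, 15, 9, 3 (total 75).
S = 75 - 1,485/36 - 1,485/30 + 75²/180 = 75 - 41.25 - 49.50 + 31.25 = 15.50.
Trend: 5 x 0.75/15.50 = 0.242. Dip: 3 x (-1.5)/15.50 = -0.290.

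The arithmetic above uses fixed authority effects. With the plan's random intercept the results are nearly the same:

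| Case | Share of one six-month trend step | Share of July-September dip |
|---|---|---|
| Planned dates | 0 | 0 |
| Any one authority +3 months, planned grid | 0.051 to 0.054 | 0 to 0.109 (absolute) |
| First authority +3 months, re-anchored | 0.215 | 0.215 |
| All five +3 months, planned grid | 0.240 | -0.288 |
| All dates and the window moved together | 0 | 0 |
| Whole six-month shift on the grid | 0 | 0 |
| Periods cut at actual go-lives, or month effects | 0 | 0 |

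If the window in case C also runs three months longer, the shares are about 0.23 and -0.28.

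**In percentage points.** A logistic version of case B gives a spurious effect of 0.11 points for an assumed trend of 0.5 points per six months, about 10% of the MDES. For 1.0 point per six months it gives 0.22 points, about 21%.

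**Precision.** With planned dates the MDES is 1.048 points with either six-month or monthly effects. With the first authority 3 months late it is 1.053 (case B), 1.060 (case A), 1.072 (monthly effects, fixed window) and 1.101 (periods cut at go-lives, moved window).

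**The case against.** The strongest objection is that the Protocol does not say how periods are cut after a date change. It does not commit to rigid six-month blocks, and the one boundary it defines, the end of baseline, is a go-live. If the other boundaries also follow actual go-lives, the leak is zero. If the planned calendar is kept, a single moved date leaks about a twentieth of a trend step. The re-anchored case gives a 33-month window that six-month blocks do not tile. Such detail may also sit in a statistical analysis plan that is not at hand. All of this stands, and it is why the result is a range.

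Several stronger readings are tempting but unsupported:

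- *A fifth of the whole trend leaks.* The share refers to the change over one six-month period, not over three years.
- *The primary estimate is biased.* The documents give no slope or season. Context says some authorities were chosen for rising looked-after rates, but not how fast these rise.
- *The 5% test rejects far too often.* The 8.8% rejection rate that case B yields needs a trend of 1 point per six months, which over 36 months adds 6 points and doubles the 6% baseline. At 0.5 points the rate is about 5.9%, and at 0.2 points about 5.15%.
- *The plan ignores the danger.* The Risks table concedes that date changes could seriously damage the analysis if not accounted for, and Randomisation requires them to be reported.

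The authority-level covariates, requested monthly, might absorb some within-period movement, but only what they happen to track. The sensitivity analyses vary the treatment definition, the test and the time since go-live; none refines the calendar adjustment.

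The objection does not remove the point. The Protocol itself fixes the moving window and the dummies, and a better time adjustment is available from dates already held.

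**Conclusion.** The point holds as a conditional weakness in the time adjustment. With the stated dummies, a go-live inside a six-month period lets part of a common trend or season into the treatment coefficient. The share is between 0 and about 0.24 of one six-month trend step, and between 0 and about 0.3 of a July-September dip, depending on which dates move and how periods are then cut. For the same event, the first authority three months late, the dip leak is +0.215 or -0.109 according to a rule the Protocol does not state.

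The shares rest on even monthly referrals, a linear approximation (the logistic trend check agrees) and illustrative three-month delays. The size in percentage points rests on assumed trends and is probably modest against the 1.05-point MDES. The change is worth making because it removes the leak at almost no cost; the documents do not show that the primary result would be invalid without it.

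**What to change.** 1. **Randomisation.** Set the start of the trial period as a fixed calendar date, six months before the first planned go-live (October 2019). State that it does not move if a go-live is re-dated, so that only the treatment indicator changes.
2. **Primary Analysis and secondary models.** Replace the five six-month dummies with one effect per calendar month of referral. Alternatively, cut the periods at every revised go-live so that treatment status is constant within each authority-by-period cell.
3. **Risks (optional).** Reconsider the Low impact rating, or point to the new time adjustment as the mitigation.

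**Cost.** This is protocol wording only; referral dates are already needed to assign treatment status. There is no loss of precision if dates hold. In the three-month example, month effects with the fixed window raise the MDES by 1-2% (1.072 against 1.060 or 1.053 points). Cutting periods at go-lives within the moved window raises it by 4-5% (1.101 against 1.053).
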